6.9 Study drug discontinuation

Patients experiencing unacceptable toxicity (AE grade 3 or higher) that the investigator considers directly attributable to the study drug should have their dose adjusted as per dose modification guidelines in Table 6-2. If a patient has already decreased 2 dose levels, no further dose reduction is permitted, and the patient will be permanently discontinued from treatment. A delay of more than 21 days in resuming study drug due to treatment-emergent adverse event will result in the withdrawal of the patient from the study (non-treatment related delay of more than 21 days but no more than 28 consecutive days may be allowed to resume therapy after discussion with the overall PI). Patient so withdrawn should undergo the required end of study procedures follow-up post treatment discontinuation.

Premature patient withdrawal/End of treatment

Patients **may** voluntarily withdraw from the study or be dropped from it at the discretion of the investigator at any time. Patients may be withdrawn from the study if any of the following occur:

- Disease progression or lack of efficacy
- Uncontrolled diabetes mellitus (DM)
- Pregnancy
- Adverse event(s)
- Abnormal laboratory value(s)
- Abnormal test procedure result(s)

QT-related discontinuation criteria

- Confirmed QTcF >480msec and discontinuation recommended by a cardiologist
- New occurrence of clinically significant/symptomatic bradycardia
- Increased risk of QT prolongation by use of QT prolonging medication
- Hypokalemia (<3.5 mmol/L) or hypomagnesaemia (<0.7 mmol/L) confirmed by repeat testing that is either a new finding or accompanied by vomiting or diarrhea and not corrected by treatment
- Protocol violation
- Subject withdrew consent
- Lost to follow-up
- Administrative problems
- Death
- Disease progression
- Treatment duration completed as per protocol

7 Visit schedule and assessments

Table 7-1 lists all of the assessments and indicates the visits at which they are to be performed with an “X”. All data obtained from these assessments must be supported in the patient’s source documentation. To accommodate scheduling challenges, the required assessments may be performed within +/- 2 days of the specified scheduled dates.

Hepatitis Screening

A detailed assessment of hepatitis B/C medical history and risk factors must be done for all patients at screening. Patients with positive hepatitis B and/or hepatitis C test results are ineligible for the study. Testing for hepatitis B viral load and serologic markers: HBV-DNA, HBsAg, HBs Ab, and HBc Ab and HCV RNA PCR are required at screening for all patients in the following risk categories:

- o All patients who currently live in (or have lived in) Asia, Africa, Central and South America, Eastern Europe, Spain, Portugal, and Greece.

[<http://wwwnc.cdc.gov/travel/yellowbook/2010/chapter-2/hepatitis-b.aspx#849>]

- o Patients with any of the following risk factors:

- known or suspected past hepatitis B infection,
- blood transfusion(s) prior to 1990,
- current or prior IV drug users,
- current or prior dialysis,
- household contact with hepatitis B infected patient(s),
- current or prior high-risk sexual activity,
- body piercing or tattoos,
- mother known to have hepatitis B
- history suggestive of hepatitis B infection, e.g., dark urine, jaundice, right upper quadrant pain.

- o Additional patients at the discretion of the investigator

Testing for hepatitis C should be performed using quantitative RNA-PCR at screening for all patients in the following risk categories:

- o known or suspected past hepatitis C infection (including patients with past interferon ‘curative’ treatment),
- o blood transfusions prior to 1990,
- o current or prior IV drug users,
- o current or prior dialysis,
- o household contact of hepatitis C infected patient(s),
- o current or prior high-risk sexual activity,
- o body piercing or tattoos,
- o At the discretion of the investigator, additional patients may also be tested for hepatitis C.

Table 7-1 Schedule of Events and Assessments

Patient assessments and the visits at which they are to be performed are indicated with an “X”. All data obtained from these assessments must be supported in the patient’s source documentation.

In order to accommodate scheduling challenges, the required assessments may be performed within +/- 2 days of the specified scheduled dates.

Examination	Screening/ Baseline	Pasireotide i.m. Everolimus p.o										End of Study	Follow-up
		1	C1D1	C1D22*	C2D1	C2D22*	C3D1	C3D22*	C4D1	C5D1	C6D1		
Visit number	1	C1D1	C1D22*	C2D1	C2D22*	C3D1	C3D22*	C4D1	C5D1	C6D1	C7D1 [§]		
Informed consent	X												
Demography	X												
History/ current medical conditions	X	X	X	X		X	X	X	X	X	X [#]	X	X
Inclusion and exclusion criteria	X												
Diagnosis and stage of cancer	X												
Prior and ongoing therapy	X ^a												X
Randomization	X												
Physical exam	X	X		X		X		X	X	X	X [#]	X	
Vital signs	X	X	X	X		X	X	X	X	X	X [#]	X	
ECG	X [*]	X	X [*]				X [*]			X [*]			
Gallbladder ultrasound	X ^b												
Performance Status	X	X		X		X		X	X	X	X [#]	X	
Hematology	X	X ^{&}		X		X		X	X	X	X [#]	X	
Glycosylated hemoglobin	X ^c	X ^{&}											
PT, PTT	X	X ^{&}											
CMP including fasting cholesterol and triglyceride [@]	X	X ^{&}		X		X		X	X	X	X [#]	X	

Table 7-1 Schedule of Events and Assessments

Patient assessments and the visits at which they are to be performed are indicated with an “X”. All data obtained from these assessments must be supported in the patient’s source documentation.

In order to accommodate scheduling challenges, the required assessments may be performed within +/- 2 days of the specified scheduled dates.

Examination	Screening/ Baseline		Pasireotide i.m. Everolimus p.o								End of Study	Follow-up	
LFT assessment ⁺	X	X	X	X	X	X		X	X	X	X [#]	X	
Hepatitis screening	X [%]												
Tumor Markers: Medullary: Free T4, TSH, CEA, Calcitonin and chromogranin A; Differentiated: TSH, free T4, thyroglobulin, thyroglobulin antibodies.	X					X			X		X [#]		
Biomarker Samples (IGF-1, optional PBMC)	X ^d					X			X		X		
Urinalysis	X	X ^{&}											
Pregnancy test	X	X ^{&}											
Archival tissue collection	X ^e												
MRI/CT Scan	X ^f					X			X		X		
Study Drug Administration		X		X		X		X	X	X	X		
Response Assessment						X			X		X		
Adverse events	X	X		X		X		X	X	X	X	X	X
Concomitant medications	X	X		X		X		X	X	X	X	X	

^s cycle 7 and beyond

& need not be repeated if within normal institutional reference limits and obtained within 7 days of C1D1

@ Albumin, alkaline phosphatase, total bilirubin, calcium, chloride, creatinine, magnesium, potassium, total protein, SGOT, SGPT, sodium, bicarbonate, total protein, total cholesterol, LDL cholesterol, HDL cholesterol, triglycerides, urea/BUN γ -GT, fasting blood glucose, phosphorous, [at screening and as clinically indicated: CPK, HbA1c, LDH lipase, α -amylase and uric acid]. If the total bilirubin concentration is increased above 1.5 times the upper normal limit (UNL), total bilirubin should be differentiated into the direct and indirect reacting bilirubin (patient may be treated if direct bilirubin is $< 1.5 \times$ UNL)

repeat visit every other cycle until progression or withdrawal from study; cholesterol and triglyceride only for patients on everolimus

* Day 22 assessments only applicable to patients on pasireotide; EKG to be obtained only for patients on pasireotide at the following timepoints

- Baseline (before pasireotide LAR injection)
- 21 days after 1st pasireotide LAR injection
- 21 days after 3rd pasireotide LAR injection
- Cycle 6 (before pasireotide LAR injection)
- Every 3 cycles after Cycle 6
- ECG should be done at any time when clinically indicated

% All patients should be screened for hepatitis risk factors and any past illnesses of hepatitis B and hepatitis C infection using clinical history as detailed in the subsection on hepatitis screening. Patients with viral hepatitis C risk factors should be screened for HCV RNA-PCR. Patients on antiviral prophylaxis treatment or positive HBV antibodies should be tested for HBV-DNA on Cycle 1 Day 1 and Day 1 of all subsequent cycles (every 28 days) to monitor for re-activation. If re-activation is confirmed, everolimus must be interrupted or discontinued according to the guidance in Tables 6-7 and 6-8. Patients with positive HCV RNA-PCR results at screening and/or a history of past infection (even if treated and considered 'cured') should have HCV RNA-PCR testing performed on Cycle 1 Day 1 and Day 1 of all subsequent cycles (every 28 days) to monitor for reactivation. Everolimus must be discontinued if HCV reactivation is confirmed according to the guidance in Table 3-4.

+: For patients receiving pasireotide, liver function tests [ALT, AST, total bilirubin, (fractionate to direct/indirect bilirubin if total bilirubin is $> 2.0 \times$ ULN), Alb, PT (INR), Alkaline Phosphatase, and GGT] must be assessed at screening, baseline (C1D1), Day 22 (C1D22) after the first injection, Day 29 (C2D1), Day 50 (C2D22), Day 57 (C3D1) and Day 85 (C4D1). After Day 85, monitoring should follow the regular CMP schedule. The Day 22 and Day 50 LFTs must be available and assessed prior to dosing on Day 29 (2nd injection) and Day 57 (3rd LAR injection).

a: not more than 1 prior systemic therapy for patients's current cancer allowed; prior radiation therapy is allowed.

b: obtain only if clinically indicated; patient found with symptomatic gallstones are excluded; patients with asymptomatic incidental gall stone may be allowed at the discretion of the PI

c: repeat as necessary if patient is a known diabetic or if baseline values elevated

d: obtain peripheral blood sample for IGF-1 at the end of every even number cycle (up to end of cycle 6) as part of restaging evaluation

e: if archival tissue cannot be obtained, upto-20 unstained slides may be collected if available.

f: same modality should be used for each restaging; other imaging studies may be obtained in addition as necessary for clinical management. **Baseline scan must be obtained not later 30 days of initiation of drug administration.**

7.1 Information to be collected on screening failures

All clinical information and results of study related procedures should be collected in the CRF for all patients who signed informed consent but later found ineligible at screening.

7.2 Patient demographics/other baseline characteristics

The study will be open to adult patients of all ethnicities, race, gender or social status who meet the eligibility criteria set forth in the protocol. Patient demographic information will be entered in the CRF at the time of enrolment.

7.3 Treatments

All current medication used to treat diabetes mellitus should be documented.

All medications, including over-the-counter medication, taken prior to study drug administration and which continue during the course of the study must be documented

Compliance will be assessed by the investigator and/or study personnel at each visit. Records of study medication used, treatment administered, and intervals between visits will be kept during the study. Drug accountability will be noted. Patients will be asked to return all used medication ampoules at each visit and the end of the study.

7.4 Efficacy

Primary efficacy assessment

The primary endpoints of this study are response rate (RR) and progression free survival (PFS). Interim analysis for the RR primary endpoint will be performed after 18 evaluable patients have been enrolled for each arm of treatment. Any arm not meeting the pre-specified efficacy RR (specified in Section 10.1 under statistical analysis) will be closed to further accrual. Tumor response assessment will be performed after every two cycles of therapy using cross-sectional imaging according to the RECIST 1.1 criteria.

All patients who completed at least 2 cycles of therapy will be deemed evaluable for the efficacy endpoint. In the event of study discontinuation prior to completing two treatment cycles for reasons other than disease progression, the affected subject will be considered inevaluable for efficacy and will be replaced by another subject (comparable as per stratification criteria) to be enrolled on the same arm of the study.

Patients who discontinue treatment due to drug-related toxicity prior to obtaining a restaging scan would be considered inevaluable and would be replaced.

Patients who discontinue treatment for symptomatic disease progression prior to a restaging scan would be deemed to have progressed as of the time of treatment discontinuation and will not be replaced.

Patients who are lost to follow-up will be censored as of the last official contact date for efficacy and survival outcome analysis. If the event occurred prior to the first restaging scan such patients will be deemed inevaluable for RR efficacy endpoint and will therefore be replaced by another

patient. They will, however, remain evaluable for overall safety assessment provided they have received at least one dose of the study drug..

Secondary efficacy assessments

Assessment for other secondary and exploratory endpoint will be performed at study conclusion.

Patient will be evaluable for overall toxicity and safety endpoint determination if they received any dose of the investigational agent.

Any patient deemed inevaluable for efficacy assessment as a result of treatment discontinuation due to treatment-related toxicity may still be evaluated for overall safety profile assessment.

Notwithstanding this provision, however, only patients who are evaluable for the primary efficacy endpoint may be included in the safety assessment conducted for the sole of picking a winning arm for the trial.

The investigational agents in this trial have not been previously studied in thyroid cancer, therefore we are unable to accurately determine the patient drop-off rate. Nonetheless, we have estimated that approximately 5% of all enrolled patients will be deemed inevaluable for safety and or efficacy assessment due to various factors listed above.

Tumor response

Response assessment will be based on the RECIST 1.1 criteria. Only patients with measurable disease at baseline should be included in the study.

Definitions

Measurable Disease - the presence of at least one measurable lesion. If the measurable disease is restricted to a solitary lesion, its neoplastic nature should be confirmed by cytology/histology.

Measurable Lesions - lesions that can be accurately measured in at least one dimension with longest diameter ≥ 20 mm using conventional techniques or ≥ 10 mm with spiral CT scan.

Non-measurable Lesions - all other lesions, including small lesions (longest diameter < 20 mm with conventional techniques or < 10 mm with spiral CT scan), i.e., bone lesions, leptomeningeal disease, ascites, pleural/pericardial effusion, inflammatory breast disease, lymphangitis cutis/pulmonis, cystic lesions, and also abdominal masses that are not confirmed and followed by imaging techniques; and:

All measurements should be taken and recorded in metric notation, using a ruler or calipers. All baseline evaluations should be performed as closely as possible to the beginning of treatment and never more than 4 weeks before the beginning of the treatment.

The same method of assessment and the same technique should be used to characterize each identified and reported lesion at baseline and during follow-up.

Clinical lesions will only be considered measurable when they are superficial (e.g., skin nodules and palpable lymph nodes). For the case of skin lesions, documentation by color photography, including a ruler to estimate the size of the lesion, is recommended.

Methods of Measurement

- CT and MRI are the best currently available and reproducible methods to measure target lesions selected for response assessment. Conventional CT and MRI should be performed with cuts of 10 mm or less in slice thickness contiguously. Spiral CT should be performed using a 5 mm contiguous reconstruction algorithm. This applies to tumors of the chest, abdomen and pelvis. Head and neck tumors and those of extremities usually require specific protocols.

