3.2 Secondary objectives

To determine the clinical benefit rate (CBR: CR + PR + SD)of everolimus, pasireotide and the combination of both agents when used as the frontline treatment for radioiodine refractory differentiated and medullary thyroid cancer.

Determine the Time to Treatment Failure (TTF) for each arm of the study

Assess the rate of and time to biochemical response using changes in serum concentrations of thyroglobulin, carcinoembryonic antigen (CEA), chromogranin A and calcitonin

To obtain additional safety data regarding concurrent and sequential administration of Everolimus and pasireotide

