4.2 Follow-up

Patients will remain on treatment and be followed at regularly scheduled office visit until treatment discontinuation due to progression, withdrawal of consent, or intolerable toxicity. Patients who discontinued therapy for reason of toxicity will be monitored at least monthly via phone or office visit until resolution of the adverse event. "All patients will be contacted for survival follow-up at least monthly via phone or office visit until death or the completion of the trial (LPLV + 30 days).

[figure not shown]

Figure 4-2: Flow diagram of the study schema, screening, stratification and randomization to one of 3 arms.

5 Population

Ninety adult patients with pathologically confirmed medullary or differentiated thyroid cancer who no longer benefit from or are intolerant of radioiodine therapy will be enrolled in the study. Patients will be enrolled across all participating sites in order of registration into the study. Patients who meet the eligibility and screening requirement will be stratified by histology, for the purposes of randomization to one of the 3 treatment arms. Patients will be randomly assigned to one of three treatment arm as described in the statistics section for a total of thirty patients in each arm.

Inclusion/exclusion criteria

The investigator or his/her designee must ensure that all patients who are offered enrollment in the study meet all of the following inclusion and exclusion criteria:

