- ii. Documentation of the qualifications, training and experience of the PI and other study staff
- iii. Eligibility of consented/enrolled patients
- iv. Informed consent document and process
- v. Verification that the local PI and staff are performing trial functions in accordance with protocol
- vi. Accuracy, completeness and timeliness of data
- vii. Accuracy and completeness of all source documentation
- viii. Response evaluation: verify that responses are identified according to the protocol definition of response for any response that is a major endpoint
- ix. Toxicity
- x. Appropriate reporting of all AEs and SAEs as required by GCP, the protocol, IRB regulations, sponsor's SOPs and other regulatory requirements

The monitor shall meet with RN/Coordinator assigned to the trial to:

provide an itemized review of the deficiencies to the RN/Coordinator and remove items from itemized review which are corrected during this meeting

review and document corrections; the RN/coordinator should indicate any remaining deficiencies and provide corrective action plan for resolution

prepare summary report for PI and Monitoring Committee to include summary of systematic deficiencies, significant protocol deviations, summary of remaining deficiencies and RN/coordinator corrective action plan, recommendations for data collection, protocol revision for clarity

The Monitor shall meet with the overall PI to discuss the report and document the PI's responses prior to submitting final report to the Monitoring Committee

The final Monitoring Committee review of audit report and PI response and PI summary of protocol to date will be included in the annual renewal submission.

Egregious data insufficiencies that may impact the scientific integrity of the trial are reported to the Medical Director and Clinical Trial Review Committee.

Please see the attached supplementary Emory University WINSHIP CANCER INSTITUTE data safety monitoring plan policy document for a complete detail of the monitoring plan.

9 Statistical methods and data analysis

All treated subjects will be included in the analysis of efficacy and safety.

Demographic and baseline characteristics will be summarized using descriptive statistics. The toxicities will be tabulated by organ system. Time to disease progression and overall survival will be evaluated using the Kaplan-Meier method.

Correlative analysis will be exploratory in the context of this Phase II screening trial.

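### The PFS analysis set is contradictory: section 7.4 makes early non-progression stops inevaluable for efficacy as a whole and replaces them, while other text keeps them in

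*Combined protocol and SAP*

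**What the plan says.** Section 7.4 (Primary efficacy assessment) names response rate (RR) and PFS as the primary endpoints. It then sets four rules for patients who leave early:

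- Any stop before two cycles "for reasons other than disease progression, the affected subject will be considered inevaluable for efficacy and will be replaced by another subject".
- For toxicity in particular: "Patients who discontinue treatment due to drug-related toxicity prior to obtaining a restaging scan would be considered inevaluable and would be replaced".
- Those who stop for symptomatic progression before a scan "would be deemed to have progressed as of the time of treatment discontinuation and will not be replaced".
- Loss to follow-up has its own rule: "Patients who are lost to follow-up will be censored as of the last official contact date for efficacy and survival outcome analysis". When a loss comes ahead of the first scan, "such patients will be deemed inevaluable for RR efficacy endpoint and will therefore be replaced by another".

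Section 7.4 does not mention death in these rules. Death does appear in the list of withdrawal reasons in section 6.9, so an early death without progression falls under the first rule.

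Two other places point the other way. Section 9 opens with "All treated subjects will be included in the analysis of efficacy and safety". Under Reporting of Results, section 7.4 has separate categories for early death from toxicity and from other causes, counts them as failures, rests conclusions on all eligible patients, and does not allow analyses that exclude early deaths or early discontinuations to support efficacy conclusions.

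The secondary objective in section 3.2 is "Determine the Time to Treatment Failure (TTF) for each arm of the study", with no event definition or analysis set. PFS events are not defined either. Section 5 plans recruitment "for a total of thirty patients in each arm", against 28 evaluable per arm in sections 4 and 9.1.

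**The concern.** A patient needs a restaging scan to be assessed for response, so an evaluability rule has some logic for RR. PFS is different: a death before the first scan is ordinarily a PFS event and needs no scan. Where the protocol limits inevaluability to RR, it does so only for patients lost to follow-up and keeps them in the time-to-event analysis as censored. Toxicity stops and deaths without progression get no such limit. Taken literally, the patients whose early exit may say something about the treatment leave PFS, and those lost to follow-up stay.

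The reach goes beyond one estimate. Under sections 4 and 9.1 the winning arm is chosen by RR, then by 1-year PFS, then by safety and tolerability. Section 7.4 limits the safety comparison used to pick a winner to patients evaluable for primary efficacy. On the literal reading, an early toxicity stop is therefore absent from all three steps. Two analysts following the same document could also report different PFS rates, and the trial is unblinded, so the choice should be fixed before outcomes are known.

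**Working it through.** **1. The rules side by side**

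| Early exit | Section 7.4, Primary efficacy assessment | Section 9 opening; 7.4 Reporting of Results |
|---|---|---|
| Toxicity stop before first scan | Inevaluable, replaced; not limited to RR | Included (treated; eligible) |
| Death without progression | Same, through the section 6.9 withdrawal list | Included; counted as a failure |
| Symptomatic progression | Event; not replaced | Included |
| Loss before first scan | Inevaluable for RR, replaced; censored in time-to-event analysis | Included |

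The first two rows conflict. The general two-cycle rule, read literally, also covers losses, so it overlaps with the specific rule for them.

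**2. Inputs**

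- 28 evaluable per arm; 1-year PFS 20% if inactive and 50% if active; 50% or more counts as sufficient activity (sections 4 and 9.1).
- Two-sided alpha 0.05, power 95% (Figure 4-1).
- 30 per arm, 90 in total (section 5).
- About 5% inevaluable; the plan says it cannot determine the drop-off rate accurately (section 7.4).

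**3. The plan's own figures**

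Enrolment: 28/(1 − 0.05) = 29.5, rounded up to 30; 3 × 30 = 90. This matches section 5.

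PFS power, one-sample normal approximation: Φ((0.30 × √28 − 1.96 × √(0.2 × 0.8)) / √(0.5 × 0.5)) = 0.946, against a stated 0.95. It reproduces.

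**4. Effect at the planned allowance**

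Let d be the share of treated patients removed and q their true 1-year PFS:

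PFS(all treated) = PFS(evaluable) × (1 − d) + q × d

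With 2 of 30 removed, d = 2/30 = 6.7%, and 50% observed in the 28 evaluable:

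- q = 0 (both fail): 0.50 × 28/30 = 14/30 = 46.7%, a shift of 3.3 points. That is 3.3/30 = 11% of the assumed 30-point difference.
- q = 50% (they do as well as the rest): 50.0%, a shift of 0.

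For scale, the standard error of 14/28 is √(0.5 × 0.5/28) = 9.4 points.

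**5. If early dropout is larger**

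Values of d above 5% are assumptions. Every removed patient is counted as a failure, so each row is an upper bound. Simple binomial proportions are used, ignoring censoring. The last column takes a true all-treated 1-year PFS of 45%, so the evaluable rate is 0.45/(1 − d), and gives the chance that the evaluable set shows at least 14/28.

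| d | Enrolled for 28 evaluable | 14/28 becomes | P(at least 14/28), true rate 45% |
|---|---|---|---|
| 0 | 28 | 50.0% | 0.36 |
| 5% | 30 | 46.7% | 0.46 |
| 10% | 32 | 43.8% | 0.57 |
| 20% | 35 | 40.0% | 0.80 |

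Against the 20% null, the exact critical value for two-sided 0.05 is 11/28. If the all-treated rate is 20%, the chance of reaching 11/28 goes from 0.015 (d = 0) to 0.021 (5%), 0.031 (10%) and 0.068 (20%), against an upper-tail limit of 0.025.

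**6. TTF**

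The shift with q = 0 is PFS(evaluable) × d, so the analogous TTF figure needs a 1-year TTF rate. The documents give neither a rate nor a definition, so none is computed.

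**The case against.** The strongest reply is that the exclusion is not the plan's settled position. A reader might infer from section 7.4 alone that early deaths are removed from PFS. The documents do not support that as a firm statement, because section 9 and the reporting rules in 7.4 would keep these patients. A narrower reading of 7.4 is also possible: the two-cycle rule follows text on the RR interim analysis and on imaging, the toxicity rule turns on the missing scan, and replacement serves the two-stage counts. This stands in part. It changes the finding from a definite exclusion to a contradiction, but it does not say which text governs. PFS is named at the head of the same subsection, and the RR limit is written only for losses.

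The size is also open to challenge, and this stands. A toxicity stop is not itself a PFS event. Table 7-1 schedules no CT or MRI at End of Study or Follow-up, so such a patient, if kept in, may be censored near baseline unless death is recorded. The 5% allowance covers every listed reason, including losses, so fewer than 2 per arm may be toxicity stops or deaths. Deaths from progression lie outside the rule altogether.

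Two stronger claims are tempting. One is that TTF is inflated by the same 3 points; without a definition or an assumed rate, that has no basis. The other is that the rule favours the combination; the direction depends on which arm has more early toxicity or death, and the documents give no comparison in these patients.

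Finally, 1-year PFS picks the winner only if RR ties or no arm reaches 3 responses. That is correct, but PFS is still a primary endpoint with its own 50% threshold.

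**Conclusion.** The concern holds as a contradiction over who is in the PFS analysis. On the restrictive reading there is also a selection effect that favours arms with more early toxicity or early death without progression. At the plan's allowance of 2 of 30 per arm, the overstatement of 1-year PFS lies between 0 and 3.3 points around a 50% rate, about a third of one standard error at the upper end. That is small, but it sits at the plan's activity threshold, and the upper bound reaches 10 points if 20% leave early. These figures assume that death counts as a PFS event, which the documents leave unsaid, and the upper bounds assume that every removed patient would have failed by 1 year. No claim is made about the size of any effect on TTF or about which arm benefits. The plan should be changed, because the choice affects a primary endpoint and can be settled before any outcome is known.

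**What to change.** In section 7.4, limit inevaluability and replacement to the Simon two-stage response count. State that PFS, and TTF once it is defined, includes every treated patient, including those who are replaced.

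Define the events: death from any cause is a PFS and TTF event on its date, and a stop for toxicity is a TTF event on the stop date. In PFS, follow toxicity stops to death through the monthly survival contact already planned in section 4.2, and to progression on any scans that are available; otherwise censor at the last tumour assessment. Then align the early-exit rules and the reporting rules in section 7.4 with the opening of section 9, and reconcile the general two-cycle rule with the rule for losses.

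The cost is modest. The response design and its 28 evaluable patients per arm are unchanged, and the survival contacts are already planned. Reported 1-year PFS becomes slightly less favourable. Progression data after a toxicity stop will be limited, because Table 7-1 schedules no scans after discontinuation; the analysis should say so.
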